Appendix 10: Management of Dermatologic Adverse Events

A. Grading and Management of futuximab/modotuximab-Related Dermatologic AEs

Recommendations for management of Grade 1 to Grade 3 futuximab/modotuximab-induced dermatologic AEs (*i.e.*, rash, xerosis, paronychia, pruritus, photosensitivity, and fissures) are summarized below. If a patient experiences any Grade 4 dermatologic AE, the patient must be withdrawn from futuximab/modotuximab treatment. It is strongly recommended that a dermatologist is consulted in the event of Grade 3 or Grade 4 dermatologic AE.

Futuximab/modotuximab - Management of Rash			
NCI-CTCAE Grade	Action with futuximab/modotuximab	Treatment- Rash	
1	Papules and/or pustules covering < 10% body surface area (BSA) , which may or may not be associated with symptoms of pruritus or tenderness	Continue at the same dose	Topical : Face and Chest Steroid creams of low potency; alclometasone 0.05% or desonide 0.05% or fluocinolone 0.01%; 2 x daily Topical : Rest-of-body moisturizers; 2 x daily Systemic ¹ : minocycline 100 mg/day or doxycycline 200 mg/day; for at least 4 weeks
2	Papules and/or pustules covering 10-30% BSA , which may or may not be associated with symptoms of pruritus or tenderness; associated with psychosocial impact; limiting instrumental activities of daily living (ADL); papules and/or pustules covering > 30% BSA with or without mild symptoms	Continue at the same dose If locally debilitating for the patient, consider following guidelines for dose-delay and dose reduction as outlined in the Dose Reduction for Grade 3 Dermatologic AEs table in Section B below	Topical : See Grade 1 Systemic ¹ : 
 - minocycline 100 mg/day or doxycycline 200 mg/day; for at least 4 weeks - 1 week course of oral steroid: methylprednisolone 4 mg tablets: 
 • Day 1: 2-1-1-2 • Day 2: 1-1-1-2 • Day 3: 1-1-1-1 • Day 4: 1-1-1 • Day 5: 1-0-1 • Day 6: 1
3	Papules and/or pustules covering > 30% BSA , with moderate or severe symptoms; limiting selfcare ADL; IV antibiotics indicated	Delay dose of futuximab/modotuximab, continue skin treatment and re-assess. Refer to the Dose Reduction for Grade 3 Dermatologic AEs table in Section B below for further guidelines on dose reduction	Topical : See Grade 1 Systemic ¹ : See Grade 2

Abbreviations (in alphabetical order): ADL, activities of daily living; BSA, body surface area; NCI-CTCAE, Common Terminology Criteria for Adverse Events v5.0

1. Alternatives in case of intolerance: First generation cephalosporins, amoxicillin, erythromycin or lincosamide.
If infection is suspected (yellow crusts, purulent discharge, painful skin/nerves): Obtain culture and change to oral antibiotic based on sensitivity

Futuximab/modotuximab - Management of Xerosis			
NCI-CTCAE Grade	Action with futuximab/modotuximab	Treatment- Xerosis	
1	< 10% BSA and no associated erythema or pruritus	Continue at the same dose	Topical : Face moisturizing cream or ointment1; 2 x daily and Topical : Body ammonium lactate 6-12% cream; 2 x daily
2	10-30% BSA and associated with erythema or pruritus; limiting instrumental ADL	Continue at the same dose If locally debilitating for the patient, consider following guidelines for dose-delay and dose reduction as outlined in the Dose Reduction for Grade 3 Dermatologic AEs table in Section B below	Topical : Face moisturizing cream or ointment1; 2 x daily and Topical : Body ammonium lactate 12% cream or salicylic acid 3-6% cream or urea 10-20% cream; 2 x daily
3	> 30% BSA and associated with pruritus; limiting self-care ADL	Delay dose of futuximab/modotuximab, continue skin treatment and re-assess. Refer to the Dose Reduction for Grade 3 Dermatologic AEs table in Section B below for further guidelines on dose reduction	Topical : Face moisturizing cream or ointment1; 2 x daily and Topical : Body ammonium lactate 12% cream or salicylic acid 3-6% cream or urea 10-20% cream; 2 x daily and Topical : Eczematous areas topical steroid (e.g., triamcinolone acetonide 0.025% or desonide 0.05% or alclometasone 0.05% or fluticasone propionate 0.05%); 2 x daily

*Abbreviations (in alphabetical order): ADL, activities of daily living; BSA, body surface area; NCI-CTCAE, Common Terminology Criteria for Adverse Events v5.0
1. If prescription is not available, recommendation by pharmacist/dermatologist is acceptable*

Futuximab/modotuximab Management of Paronychia		
NCI-CTCAE Grade	Action with futuximab/modotuximab	Treatment- Paronychia
1	Nail fold edema or erythema; disruption of the cuticle	Continue at the same dose Topical: antibiotics (e.g., clindamycin 1% or erythromycin 1%) and vinegar soaks (i.e., soaking fingers or toes in a 1:1 solution of white vinegar in water for 15 min daily)
2	Localized intervention indicated; oral intervention indicated (e.g., antibiotic, antifungal, antiviral); nail fold edema or erythema with pain; associated with discharge or nail plate separation; limiting instrumental ADL	Continue at the same dose If locally debilitating for the patient, consider following guidelines for dose-delay and dose reduction as outlined in the Dose Reduction for Grade 3 Dermatologic AEs table in Section B below Topical: silver nitrate application weekly (consultation with dermatologist or surgeon is recommended) and Systemic: bacterial culture, oral antibiotic if infection confirmed
3	Operative intervention indicated; IV antibiotics indicated; limiting self-care ADL	Delay dose of futuximab/modotuximab, continue skin treatment and re-assess. Refer to the Dose Reduction for Grade 3 Dermatologic AEs table in Section B below for further guidelines on dose reduction Topical: silver nitrate application weekly (consultation with dermatologist or surgeon is recommended) and consider nail avulsion (consultation with dermatologist or surgeon is recommended) and Systemic: bacterial culture, oral antibiotic if infection confirmed

Abbreviations (in alphabetical order): ADL, activities of daily living; NCI-CTCAE, Common Terminology Criteria for Adverse Events v5.0; IV, intravenous

Futuximab/modotuximab Management of Pruritus		
NCI-CTCAE Grade	Action with futuximab/modotuximab	Treatment- Pruritus
1	Mild or localized; topical intervention indicated	Continue at the same dose Topical: steroid (e.g., triamcinolone acetonide 0.025%, desonide 0.05%, alclometasone 0.05%, Fluticasone propionate 0.05%); 2 x daily or anti-pruritics (e.g., pramoxine 1%, doxepin 5% cream); 2 x daily
2	Widespread and intermittent; skin changes from scratching (e.g., edema, papulation, excoriations, lichenification, oozing/crusts); oral intervention indicated; limiting instrumental ADL	Continue at the same dose If locally debilitating for the patient, consider following guidelines for dose-delay and dose reduction as outlined in the Dose Reduction for Grade 3 Dermatologic AEs table in Section B below Systemic: oral antihistamines (diphenhydramine 25-50 mg; hydroxyzine 25 mg; fexofenadine 60 mg; 3 x daily)
3	Widespread and constant; limiting self care ADL or sleep; systemic corticosteroid or immunosuppressive therapy indicated	Delay dose of futuximab/modotuximab, continue skin treatment and re-assess. Refer to the Dose Reduction for Grade 3 Dermatologic AEs table in Section B below for further guidelines on dose reduction Same as for Grade 2

Abbreviations (in alphabetical order): ADL, activities of daily living; NCI-CTCAE, Common Terminology Criteria for Adverse Events v5.0

Futuximab/modotuximab Management of Photosensitivity		
NCI-CTCAE Grade	Action with futuximab/modotuximab	Treatment- Photosensitivity
1	Painless erythema and erythema covering <10% BSA	Continue at the same dose Topical: broad spectrum sunscreen with an SPF of at least 15; reapplied every 2 hours or more frequently if swimming or perspiring and Systemic: bacterial culture, oral antibiotic if infection confirmed
2	Tender erythema covering 10-30% BSA	Continue at the same dose If locally debilitating for the patient, consider following guidelines for dose-delay and dose reduction as outlined in the Dose Reduction for Grade 3 Dermatologic AEs table in Section B below Topical: corticosteroids (e.g., triamcinolone acetonide 0.025% or desonide 0.05% or alclometasone 0.05% cream or fluticasone propionate 0.05%); 2 x daily
3	Erythema covering > 30% BSA and erythema with blistering; photosensitivity; oral corticosteroid therapy indicated; pain control indicated (e.g., narcotics or NSAIDs)	Delay dose of futuximab/modotuximab, continue skin treatment and re-assess. Refer to the Dose Reduction for Grade 3 Dermatologic AEs table in Section B below for further guidelines on dose reduction Same as for Grade 2

Abbreviations (in alphabetical order): BSA, body surface area; NCI-CTCAE, Common Terminology Criteria for Adverse Events v5.0; NSAID, nonsteroidal anti-inflammatory drug; SPF, sun protection factor

Futuximab/modotuximab Management of Fissures		
NCI-CTCAE Grade	Action with futuximab/modotuximab	Treatment- Fissures
1	Initiated at first occurrence	No action Topical: - thick moisturizers of zinc oxide (13-40%) cream - liquid glues of cyanoacrylate to seal cracks
2	If no improvement after 2 weeks from initiation of Step 1	No action Topical: - thick moisturizers of zinc oxide (13-40%) cream under occlusion at night - salicylic acid 6% cream or ammonium lactate/lactic acid 12%
3	If no improvement after 2 weeks from initiation of Step 2	Delay dose of futuximab/modotuximab, and re-assess. Discuss need for dose reduction and/or further dose omissions with sponsor or designee Continue local treatment as described in Step 2

Prophylaxis for fissures includes careful use of moisturizing creams and/or ointments 3 times a day and after handwashing, using only fragrance-free soaps. Should fissures begin to form, a stepwise approach outlined above should be followed. **Topical application of cyanoacrylate tissue adhesive (i.e., surgical glue) products may be considered to promote wound repair.**

If fissures occur which are unresponsive to intensive therapeutic treatment as specified above, futuximab/modotuximab dosing should be delayed. The need for dose-reduction and/or continued dose-delays should be discussed with the sponsor or designee, if adequate improvement is not seen after the initial dose-delay.

B. Dose Reduction Guidelines for futuximab/modotuximab-Related Dermatologic AEs

Dose delay and/or intrapatient dose reduction(s) will be required upon occurrence of Grade 3 anti-EGFR associated dermatologic AE, and should be implemented according to Table Dose Reduction for Grade 3 Dermatologic AEs

Futuximab/modotuximab Dose Reduction for Grade 3 Dermatologic AEs			
Dermatologic AE Grade 3	Futuximab/modotuximab Immediate Action	Outcome Improvement	Futuximab/modotuximab
First occurrence	Delay dose	Grade \leq 1	Continue at same dose
		Grade 2	Reduce to 4.5 mg/kg
		No improvement	Discontinue
Second occurrence	Delay dose	Grade \leq 1	Continue at same dose
		Grade 2	At dose of 6.0 mg/kg: Reduce to 4.5 mg/kg At dose of 4.5 mg/kg: Reduce to 3.0 mg/kg
		No improvement	Discontinue
Third occurrence	Delay dose	Grade \leq 1	Continue at same dose
		Grade 2	At dose of 6.0 mg/kg: Reduce to 4.5 mg/kg At dose of 4.5 mg/kg: Reduce to 3.0 mg/kg At dose of 3.0 mg/kg: discontinue
		No improvement	Discontinue
Fourth occurrence	Discontinue	Any	Discontinue

Abbreviations (in alphabetical order): AE, adverse event; kg, kilogram; mg, milligram
Note: Dose reductions for 9 mg/kg loading not applicable. For dose delays, re-assess after < 2 weeks. Longer delays are allowed if no recovery to < Grade 2 after 2 weeks

In each case, the next treatment should be delayed, and the patient's condition should be reassessed after 1 week, and if necessary, 2 weeks. Treatment should be delayed further if the AE remains at Grade 3 after 2 weeks.

In the case of a Grade 2 dermatologic AE which is locally debilitating for the patient, the guidelines outlined above may be followed at the investigator's discretion.

Participants must be withdrawn from futuximab/modotuximab treatment in the event of a Grade 4 dermatologic AE.

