8.11.2.3. Dose Reduction

In the event of Grade 3 treatment-related AEs, the participant may continue on study if there is evidence of clinical benefit as judged by the treating physician, but could do so at a reduced dose of futuximab/modotuximab once retreatment criteria are met ([Section 6.1.5](#)) (specific instructions for dose reduction linked to IRR, dermatologic AEs, and hypomagnesemia, are provided in Appendices 9, 10 and 11, respectively). All dose reductions of futuximab/modotuximab must be documented on the appropriate page of the participant's e-CRF.

If toxicity is to be managed by dose reduction, the futuximab/modotuximab dose will be decreased as shown in ([Table \(8.11.2.3\) 1](#)). Dose reduction may occur either during treatment cycles, or between cycles, as clinically indicated.

Table (8.11.2.3) 1 - Dose reduction of futuximab/modotuximab

Starting dose (Dose level 0)	Dose level -1	Dose level -2
Futuximab/modotuximab*	6 mg/kg	4.5 mg/kg

*Note: Dose Reductions for 9 mg/kg loading dose not applicable. The number of dose reductions allowed is limited to 2

Abbreviations (in alphabetical order): kg, kilogram; mg, milligram

A maximum of 2 dose reductions for futuximab/modotuximab-related toxicity are allowed (to a minimum dose of 3 mg/kg). Do not re-escalate dose after it has been reduced.

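### The Appendix 10 fissure table sets dosing by elapsed time, so for a Grade 3 fissure it contradicts the mandatory Grade 3 dermatologic rule

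*Protocol*

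**What the plan says.** Protocol Appendix 10, Part A opens by naming six types of dermatologic event, fissures among them, for which it gives Grade 1 to 3 management. A table follows for each.

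For rash, xerosis, paronychia, pruritus and photosensitivity, the rows are defined by severity. Each Grade 3 row delays the dose and then says: "Refer to the Dose Reduction for Grade 3 Dermatologic AEs table in Section B below for further guidelines on dose reduction".

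The fissure table works differently. Row 1 starts at first occurrence. Row 2 applies after 2 weeks without improvement on Step 1. Row 3 applies "If no improvement after 2 weeks from initiation of Step 2". Rows 1 and 2 call for no action on futuximab/modotuximab. Row 3 delays the dose, asks for reassessment and adds: "Discuss need for dose reduction and/or further dose omissions with sponsor or designee". The text below the table says: "Should fissures begin to form, a stepwise approach outlined above should be followed". If a first delay does not help, it continues: "The need for dose-reduction and/or continued dose-delays should be discussed with the sponsor or designee".

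Part B of the appendix states the general rule: "Dose delay and/or intrapatient dose reduction(s) will be required upon occurrence of Grade 3 anti-EGFR associated dermatologic AE". Section 8.12.5 repeats that requirement in the protocol body. The Part B table gives dose delay as the immediate action at the first three occurrences. It then fixes what follows: same dose if the event improves to Grade 1 or less, reduction if it improves to Grade 2, discontinuation if it does not improve.

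**The concern.** A fissure can be Grade 3 when it first appears, or become so during Step 1 or Step 2. The fissure table then tells the site to leave the antibody dose alone, while Part B and Section 8.12.5 require delay and/or reduction at once. At Step 3 both routes delay the dose, but Part B prescribes the next decision and the fissure text refers it to the sponsor.

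The protocol does not say which instruction prevails. A site could reasonably take the fissure table as a deliberate exception, because the pointer to Part B appears in five tables and is replaced by a different instruction in the sixth. Two sites could then treat the same Grade 3 fissure differently. What is at stake is participant safety and consistent dosing across sites. Efficacy endpoints, analyses and the DLT definition are untouched.

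**Working it through.** The check is mainly a comparison of texts; the plan gives no figure of its own to reproduce.

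**1. Is a Grade 3 fissure within scope?** Yes. The introduction to Part A lists fissures among the dermatologic events managed from Grade 1 to Grade 3. Neither Part B nor Section 8.12.5 exempts them.

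**2. Which Part A tables send Grade 3 to Part B?**

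| Table | Row trigger | Antibody action in rows 1-2 | Row 3 | Pointer to Part B at Grade 3 |
|---|---|---|---|---|
| Rash | severity | same dose | delay | yes |
| Xerosis | severity | same dose | delay | yes |
| Paronychia | severity | same dose | delay | yes |
| Pruritus | severity | same dose | delay | yes |
| Photosensitivity | severity | same dose | delay | yes |
| Fissures | time | none | delay, then sponsor discussion | no |

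The count is 5 of 6. For the fissure rows I rely on the row text, which itself speaks of Steps 1 and 2, and on the prose below the table. I do not rely on the column heading, which may be an artefact of reading the table.

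**3. Timing.** Earliest Step 3 = 14 days (Step 1) + 14 days (Step 2) = 28 days after Step 1 starts. Under the Part B table, delay is immediate.

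**4. Worst-case exposure if a site follows only the fissure table.** Inputs: weekly infusions on D1, D8, D15 and D22 (Section 6.1.1.3); maintenance dose 6 mg/kg (Section 6.1.1.1); retreatment criteria applied after a delay and before each cycle, not at the weekly visits within a cycle (Section 6.1.5). Assume that Step 1 starts with the Grade 3 event, that the event stays at Grade 3, and that the dose has not already been reduced.

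| Grade 3 starts | Remaining infusions in the cycle | Dose |
|---|---|---|
| after D1 | D8, D15, D22 | 3 × 6 = 18 mg/kg |
| after D8 | D15, D22 | 2 × 6 = 12 mg/kg |
| after D15 | D22 | 1 × 6 = 6 mg/kg |
| after D22 | none | 0 |

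The next cycle start is then blocked by Section 6.1.5 while the related event remains at Grade 3. Under Part B the number is 0 until reassessment.

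**5. How common are fissures?** Section 2.8 reports skin fissures of any grade in 10 of 20 patients (50%) on the 9/6 mg/kg regimen in the Phase 1 expansion. The Grade 3 share is not given.

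**The case against.** The strongest reply is that the Grade 3 rule plainly governs. Part B and Section 8.12.5 are worded as requirements, while the Part A guidance is called recommendations. Section 8.11.2.3 points the same way: after a related Grade 3 event a participant may stay on study, but "could do so at a reduced dose of futuximab/modotuximab once retreatment criteria are met". On that reading only a cross-reference is missing. This is probably the intent, but it does not settle the matter. Section 8.11.2.3 also says that "specific instructions for dose reduction linked to IRR, dermatologic AEs, and hypomagnesemia, are provided in Appendices 9, 10 and 11", which returns the reader to the appendix that contains both instructions.

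A second reply is that the rows could be read as Grades 1, 2 and 3, which would remove most of the conflict. The row text rules this out: each later row depends on 2 weeks without improvement on the step before.

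A third is that Step 3 is compatible with Part B. This is partly right. Both delay the dose, and Part B is not rigid: the text below its table allows further delay while the event is still Grade 3 after 2 weeks. The clear contradiction lies in Steps 1 and 2. At Step 3 the difference is between a prescribed decision and an open one.

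The limits on reach also stand. The worst case requires a site to disregard Section 8.12.5, Part B and Section 8.11.2.3. It also runs against the weekly dermatologic examinations and the advice to consult a dermatologist at Grade 3. In Cycle 1 of the Safety Lead-In, a Grade 3 fissure counted as a DLT under the general non-haematologic criterion must lead to delay (Sections 4.1.3.2 and 4.1.3.3). SAP Section 1 records that the randomised part was cancelled, which reduces the number who could be exposed. None of this removes the contradiction from the protocol text.

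**Conclusion.** The concern holds. For a Grade 3 fissure, Steps 1 and 2 of the fissure table contradict Appendix 10 Part B and Section 8.12.5, and Step 3 leaves open a dose decision that the Part B table fixes. Grade 1-2 fissures are not in conflict, and Grade 4 is covered by the stated withdrawal rule.

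The size is a delay that comes at the earliest 28 days after Step 1 starts instead of at once, and at most 3 extra infusions (18 mg/kg). That maximum rests on the assumptions listed in the check and on a site following the fissure table alone. The number of participants affected cannot be estimated from the documents. This should be fixed as a matter of dosing safety and consistency between sites; no statistical result depends on it.

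**What to change.** In the Appendix 10 Part A fissure table:

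- Label the rows as steps.
- Limit the stepwise antibody instructions, and the paragraph below the table that refers reduction to the sponsor, to Grade 1-2 fissures. Keep Part B optional for a locally debilitating Grade 2 fissure.
- Add a line covering all steps: *Any Grade 3 fissure: follow the Section B table from onset, whatever the step; Grade 4: withdraw from futuximab/modotuximab.*
- Leave the topical treatment as it is.

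The cost is a wording change to one table and one paragraph, with no added data, visits or participants.

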8.11. Management of treatment dose adaptations due to toxicities

For participants who have experienced a dosing modification, reasons for dose modifications or delays, the supportive measures taken, and the outcome will be documented in the participant's source documents and recorded in the e-CRF.

In the futuximab/modotuximab plus trifluridine/tipiracil arm doses of either futuximab/modotuximab, or trifluridine/tipiracil, or both drugs can be modified, depending on the toxicity observed.

General rules:

Before starting a new treatment cycle, toxicity must have resolved as specified in the [Sections 8.11.1](#) and [8.11.2](#) and the safety criteria to be met as specified in the [Section 6.1.5](#).

- If toxicity due to any of the IMPs does not resolve during the given cycle to Grade 1 or baseline, the start of the next cycle will be delayed for a maximum of 30 days for trifluridine/tipiracil and 21 days for futuximab/modotuximab (see [Sections 8.11.1](#) and [8.11.2](#)). If more than the maximum delay period is needed for recovery, the next cycle should be started with the IMP not concerned by the toxicity.
- If, in the opinion of the investigator, the toxicity is clearly related to one of the treatments, reduction of one and not the other agent is appropriate. If, in the opinion of the investigator, the toxicity is related to the futuximab/modotuximab only futuximab/modotuximab should be reduced according to recommended dose modifications. If, in the opinion of the investigator, the toxicity is related to the trifluridine/tipiracil only trifluridine/tipiracil should

be reduced according to recommended dose modifications. If the toxicity is related to the combination of two agents, both agents should be reduced (if applicable), interrupted or discontinued according to the recommended dose modifications.

- Participants may have trifluridine/tipiracil discontinued and continue on futuximab/modotuximab alone. Similarly, participants may discontinue futuximab/modotuximab and continue on trifluridine/tipiracil alone if appropriate.

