8.11.2.2. Dose Delay

Toxicities may be managed by delay in dosing, provided they do not meet the criteria for IMP discontinuation ([Section 5.8.1](#)). In such cases, the period between any 2 scheduled doses may be extended up to 3 days (inclusive) to allow an improvement of the toxicity. Such delays will be considered an extension within the current cycle. If a delay of more than 3 days from the scheduled dose date is necessary, the dose should be omitted and proceed to the next scheduled dose (i.e. 14 days from the last dose).

If 3 consecutive doses are needed to be omitted (i.e. more than 21 days from the last dose of futuximab/modotuximab), the participant should be discontinued from futuximab/modotuximab. All delays of futuximab/modotuximab must be documented on the appropriate page of the participant's e-CRF.

If toxicity does not resolve during the given cycle to Grade 1 or baseline, the start of the next cycle may be delayed by a maximum of 21 days from the last dose of futuximab/modotuximab administered to allow the initiation of both IMPs at the same time in the next cycle. If more than 21 days from the last dose administered are needed for recovery, futuximab/modotuximab should be discontinued and the next cycle will start with only trifluridine/tipiracil.

Dosing may be restarted at the same dose, as clinically indicated. However, administration of futuximab/modotuximab may only be restarted provided retreatment criteria are met ([Section 6.1.5](#)).

For treatment restart with no dose reduction:

- If treatment restart after the omission of 1 dose (i.e. treatment delay up to 14 days from the last dose), it is recommended that dosing restart with maintenance dose of 6 mg/kg;
- If treatment restart after the omission of 2 consecutive doses (i.e. treatment delay up to 21 days from the last dose), it is recommended that dosing re-start with the re-administration of a loading dose of 9 mg/kg followed by weekly maintenance doses of 6 mg/kg.

For treatment restart with dose reduction, see Section 8.11.2.3.

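### For a skin AE still at Grade 3 after 2 weeks, Appendix 10 extends the delay with no maximum duration while 8.11 and 8.11.2.2 cap it at 21 days, and no text says which prevails (minor: Grade 1 infusion-reaction rules also differ)

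*Protocol*

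**What the plan says.** **Persisting Grade 3 skin AE, Appendix 10, part B.** Delay or dose reduction is required and "should be implemented according to Table Dose Reduction for Grade 3 Dermatologic AEs". In that table, no improvement leads to discontinuation at the first, second and third occurrence, with no time at which improvement is judged. The text below the table has the participant "reassessed after 1 week, and if necessary, 2 weeks", and then: "Treatment should be delayed further if the AE remains at Grade 3 after 2 weeks". The table note adds: "Longer delays are allowed if no recovery to < Grade 2 after 2 weeks". None of these gives a maximum length of delay.

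**Persisting toxicity, main body.** Under the general rules of 8.11, "the start of the next cycle will be delayed for a maximum of 30 days for trifluridine/tipiracil and 21 days for futuximab/modotuximab". Beyond that, the next cycle starts with the other drug. Section 8.11.2.2 counts from the last dose: "If more than 21 days from the last dose administered are needed for recovery, futuximab/modotuximab should be discontinued". It applies the same consequence to omitted doses: "If 3 consecutive doses are needed to be omitted (i.e. more than 21 days from the last dose of futuximab/modotuximab"). It also defines omission: "If a delay of more than 3 days from the scheduled dose date is necessary, the dose should be omitted".

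**Routing between them.** Section 8.11.2 sends temporary delay to 8.11.2.2. Section 4.1.3.3 sends the conditions for resuming after a DLT to 8.11, and Table (4.1.3.2) 1 makes Grade 3 skin toxicity lasting more than 2 weeks a DLT. Section 8.11.2.3 cites Appendix 10 for dose reduction only, but 8.12.5 cites it for the management of dermatologic AEs generally.

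**Grade 1 infusion reaction (minor).** Section 8.12.4.1 makes a 50% rate decrease mandatory and keeps the lower rate for all later infusions. Appendix 9, part C, asks the investigator only to consider it, and carries the slower rate forward only if the infusion was extended.

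**The concern.** A site with a participant whose rash is still Grade 3 at the 2-week check finds one text that tells it to go on delaying and another that tells it to end futuximab/modotuximab once a fixed interval has passed. Two sites could treat identical participants differently, each in line with a passage of the protocol.

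The stake is whether the drug is permanently stopped or held with restart still possible. This bears on three planned outputs:

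- Delays and permanent stops are both components of the Safety Lead-In primary endpoint (Protocol Table (3.4) 1).
- SAP 3.5.1 describes delay and withdrawal separately.
- SAP 5.2.1.2 has a deviation category for participants who met a withdrawal criterion but stayed on treatment. Counting them requires knowing which rule is the criterion.

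For the infusion-reaction mismatch, the SAP 3.3.1.2 count of participants with a decreased infusion rate depends on which section the site followed.

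**Working it through.** **Inputs**

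- Weekly dosing, ±2 days (Protocol 6.1.1.3).
- Reassessment at 1 and 2 weeks, then further delay (Appendix 10, part B).
- Limit of 21 days from the last dose; a dose is omitted once delayed by more than 3 days (8.11.2.2).
- Volume 250 mL for a 6 mg/kg dose (6.1.1.5), maximum rate 500 mL/h (6.1.1.6).

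**Step 1: reproduce the plan's own figures.** Take the last dose as day 0, so scheduled doses fall on days 7, 14, 21 and 28. One omission means restart on day 14, two mean day 21, and three mean day 28, which exceeds 21. This matches the 14-day and 21-day figures in 8.11.2.2.

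**Step 2: place the 2-week reassessment on that calendar.** Appendix 10 does not say when its clock starts, so let it start d days after the last dose. This is an assumption, and the range is shown.

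- Reassessment day = d + 14
- Days left before the limit = 21 − (d + 14) = 7 − d

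| Clock start d | Reassessment day | Days left |
|---|---|---|
| 0 | 14 | 7 |
| 5 (dosing visit 2 days early) | 19 | 2 |
| 6 | 20 | 1 |
| 7 (next weekly dose) | 21 | 0 |
| 9 (dosing visit 2 days late) | 23 | −2 |

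**Step 3: read the conflict.** At d = 7 any further delay exceeds 21 days from the last dose. If it runs more than 3 days past day 21, the day-21 dose also becomes the third consecutive omitted dose (days 7, 14, 21), so both discontinuation triggers in 8.11.2.2 are met. At d = 0 to 6, a further delay of up to 7 to 1 days satisfies both texts, and the conflict arises only beyond that. Section 8.11 does not state where its own 21 days start; the calendar above uses the 8.11.2.2 definition.

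**Step 4: check dosing.** The retreatment criteria in 6.1.5 apply after any dose delay. For IMP-related clinical events they require Grade 1 or lower, return to baseline, resolution, or adequately controlled Grade 2. A related skin AE still at Grade 3 fails them under either text.

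**Step 5: infusion reaction.** After a Grade 1 reaction at 500 mL/h, a later complete 6 mg/kg infusion takes 250 / 250 = 1 h = 60 min under 8.12.4.1. Under Appendix 9 it may stay at 250 / 500 = 0.5 h = 30 min if the site does not slow it.

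**The case against.** The best defence is that the texts can be read together. Section 8.11.2 assigns delay to 8.11.2.2, and 8.11.2.3 cites Appendix 10 for dose reduction only, so the body would fix how long a delay may last and the appendix the dose afterwards. For a Cycle 1 DLT, which covers Grade 3 skin toxicity lasting more than 2 weeks, 4.1.3.3 names 8.11. Appendix 10 never says that a delay may pass 21 days, so a site could delay further up to the cap.

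This has weight, but it does not settle the matter. Section 8.12.5 refers management of dermatologic AEs to Appendix 10, and Appendix 10 itself gives instructions on delay. At the ordinary weekly visit (d = 7) no days remain in which to delay further up to the cap. No passage states precedence or mentions the cap beside the skin rules.

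Three stronger inferences are tempting, and the documents do not support them:

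- *That Appendix 10 provides no end to the delay.* Its table discontinues for no improvement. What is missing is a maximum duration and a time for that judgement.
- *That one reading re-doses a participant with persisting Grade 3 toxicity.* Section 6.1.5 prevents this on both readings.
- *That the results are distorted.* SAP 3.5.1 tabulates the actions recorded, so the wording affects what sites do, not how a recorded action is classified. No affected case is shown.

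On the infusion reaction, 8.12.4 and Appendix 9 both defer to the investigator's best clinical judgment, which softens the mismatch without removing it.

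**Conclusion.** The point holds as an unreconciled pair of rules on how long futuximab/modotuximab may be withheld for a Grade 3 skin AE that persists after 2 weeks. The size depends on the undefined clock: the texts collide at once if it starts at the next weekly dose or later, and after 1 to 7 further days if it starts on days 6 to 0. The practical difference is permanent stop versus continued delay with later restart possible. How the table's no-improvement row relates to the instruction to delay further is also unclear; this is an ambiguity in timing, not a proven contradiction.

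The Grade 1 infusion-reaction mismatch is real but minor.

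The documents do not say how often Grade 3 skin AEs fail to resolve, so no frequency is claimed. Reach is limited: SAP section 1 records that the study was discontinued during the Safety Lead-In for strategic reasons and the randomised part cancelled. The conflict does not alter the DLT definition or the planned sample size, power or alpha.

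**What to change.** The sponsor should reconcile Appendix 10, part B (table, note and text) with 8.11 and 8.11.2.2. The reconciled text should state when the 2-week clock starts, when lack of improvement is judged, how both relate to the 21-day limit, and which section governs skin AEs. Section 8.12.4.1 and Appendix 9, part C, should likewise be brought into line for Grade 1 infusion reactions. Body and appendix should then carry one identically worded rule for each situation. Which rule applies is for the sponsor to decide.

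The cost is a protocol wording amendment, with no added procedures, visits or participants.
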